12.12 List of Abbreviations and Definition of Key Study Terms

List of Abbreviations

| Abbreviations | Description of abbreviations |
|----------------------|--|
| AE | adverse event |
| ALP | alkaline phosphatase |
| ALT | alanine aminotransferase |
| AST | aspartate aminotransferase |
| bpm | Beats per minute |
| BUN | blood urea nitrogen |
| CA | Competent authority |
| CBC | complete blood count |
| CCSI | company core safety information |
| CI | Confidence interval |
| C _{max} | maximum concentration |
| CPAP | Continuous Positive Airway Pressure |
| CRF | case report form |
| CRO | contract research organization |
| CSR | Clinical study report |
| CTCAE | common terminology criteria for adverse events |
| CTMP | Chronic Tympanic Membrane Perforation |
| CV | Coefficient of variation |
| dB | Decibels |
| DEC | Dose Escalation Committee |
| DILI | drug-induced liver injury |
| DMC | Data Monitoring Committee |
| DPD | Data Protection Directive |
| eCRF | electronic case report form |
| EC ₅₀ | Effective Concentration |
| ECV | Equivalent Ear Canal Volume |
| EEA | European Economic Area |
| EGF | Epidermal growth-like factor |
| EMA | European Medicines Agency |
| EOS | End of Study |
| FAS | full analysis set |
| GCP | Good Clinical Practice |
| GCPL | Global Pharmacology Lead |
| GML | Global Medical Lead |

| Abbreviations | Description of abbreviations |
|----------------------|---|
| GMP | Good Manufacturing Practices |
| GGT | gamma-glutamyltransferase |
| Hz | hertz |
| IAP | Interim Analysis Plan |
| IB | Investigational Brochure |
| ICE | Intercurrent event |
| ICF | informed consent form |
| ICH | International Council for Harmonisation of Technical Requirements for Pharmaceuticals for Human Use |
| IEC | Independent Ethics Committee |
| IP | investigational product |
| IMP | investigational medicinal product |
| IRB | Institutional Review Board |
| IRT | interactive response technology |
| ISN | international study number |
| kHz | kilohertz |
| LA-CRF | liver abnormality case report form |
| LS | Least square |
| MAD | Multiple Ascending Dose |
| MAR | Missing at random |
| MEDRA | Medical Dictionary for Regulatory Activities |
| MH | Mantel-Haenszel |
| MID | Minimum Intolerable Dose |
| mL | milliliter |
| mm | Millimeters |
| mmHg | Millimeters of mercury |
| MMRM | mixed models repeated measures |
| MTD | Maximum tolerated dose |
| NOAEL | No observed adverse event level |
| PD | protocol deviation |
| PET | Positron emission tomography |
| PK | Pharmacokinetic |
| PTA | Pure Tone Audiometry |
| PT | Preferred Term |
| QA | quality assurance |
| QC | quality control |
| RBC | red blood cell |

| Abbreviations | Description of abbreviations |
|----------------------|--|
| RNA | Ribonucleic acid |
| RSI | reference safety information |
| (S)AE | serious adverse event or adverse event |
| SAD | Single Ascending Dose |
| SAE | serious adverse event |
| SAF | Safety analysis set |
| SAP | Statistical analysis plan |
| SDV | source document verification |
| SE | Standard error |
| SFL | screen failure log |
| SOC | System organ class |
| SOP | standard operating procedure |
| SPC | summary of product characteristics |
| SUSAR | suspected unexpected serious adverse reactions |
| TEAE | treatment-emergent adverse event |
| TBL | total bilirubin |
| TM | Tympanic membrane |
| TMF | Trial Master File |
| TMP | Tympanic membrane perforation |
| TVAS | Tinnitus visual analog scale |
| ULN | upper limit of normal |
| USM | Urgent safety matter |
| WBC | white blood cell |
| WOCBP | Women of child bearing potential |
| µg | microgram |

Definition of Key Study Terms

| Terms | Definition of Terms |
|------------------------|---|
| Baseline | Assessments of subjects as they enter a study before they receive any treatment. |
| Endpoint | Variable that pertains to the efficacy or safety evaluations of a study. Note: Not all endpoints are themselves assessments since certain endpoints might apply to populations or emerge from analysis of results. That is, endpoints might be facts about assessments (e.g., prolongation of survival). |
| Enroll | To register or enter a subject into a study. Note: Once a subject has received the IP or placebo, the protocol applies to the subject. |
| Intervention | The drug, device, therapy or process under investigation in a study that is believed to have an effect on outcomes of interest in a study (e.g., health-related quality of life, efficacy, safety and pharmacoeconomics). |
| Investigational period | Period of time where major interests of protocol objectives are observed, and where the test product or comparative drug (sometimes without randomization) is given to a subject and continues until the last assessment after completing administration of the test product or comparative drug. |
| Randomization | The process of assigning subjects to treatment or control groups using an element of chance to determine assignments in order to reduce bias. NOTE: Unequal randomization is used to allocate subjects into groups at a differential rate; for example, three subjects may be assigned to a treatment group for every one assigned to the control group. |
| Screening | A process of active consideration of potential subjects for randomization in a study. |
| Screen failure | Potential subject who signed the ICF, but did not meet 1 or more criteria required for participation in the study and was not randomized. |
| Screening period | Period of time before entering the investigational period, usually from the time when a subject signs the consent form until just before the test product or comparative drug (sometimes without randomization) is given to a subject. |
| Study period | Period of time from the first study site initiation date to the last study site completing the study. |
| Variable | Any quantity that varies; any attribute, phenomenon or event that can have different qualitative or quantitative values. |

13 PROTOCOL AMENDMENT SUMMARY OF CHANGES

ISN/Protocol 0598-CL-0101 A Phase 1/2, Randomized, Placebo-controlled Study to Assess the Safety, Tolerability, Efficacy, and Pharmacokinetics of ASP0598 Otic Solution Following Topical Application into the Ear in Subjects with Chronic Tympanic Membrane Perforation (CTMP)

Amendment 4 [Nonsubstantial] 29 Aug 2022

This amendment is considered to be nonsubstantial based on the criteria set forth in Article 10(a) of Directive 2001/20/EC of the European Parliament and the Council of the European Union because it neither significantly impacts the safety or physical/mental integrity of participants nor the scientific value of the study.

Overall Rationale for the Amendment:

Language was revised in the protocol to offer the elderly population more opportunity to participate in this First In Human study.

Summary of Changes

Table 1 Nonsubstantial Changes

| Section Number | Description of Change | Brief Rationale |
|----------------|---|--|
| Synopsis | The planned study period is updated to end 3Q2024. | To update the study period according to the latest timeline. |
| Synopsis, 5.1 | Inclusion criterion #2 is updated to allow for enrollment of subjects 18 to 75 years of age. | To allow a more elderly population to participate in the study after the study team identified a significant unmet need based on study site feedback. Considering this is the First In Human study, an upper age limit was included based on the predicted mechanisms of action. There is no safety concern for increasing the upper age limit given the nature of the CTMP patient population and the observed safety data to date. |
| 7.6 | Add that for MAD cohorts only, the total amount of whole blood collected will be approximately 30.0 mL per subject. | To reflect the correct amount of blood sample taken for MAD cohorts. |
| Throughout | Minor administrative-type changes, e.g., typos, format, numbering, consistency throughout the protocol. | To provide clarifications to the protocol and to ensure complete understanding of study procedures. |

6.9.2	Analysis Windows for Efficacy Variables	37
6.9.3	Imputation Rules	39
7	REVISION AND RATIONALE	42
7.1	List of Changes in SAP Version 3.0 from Version 2.0	42
7.2	List of Changes in SAP Version 2.0 from Version 1.0	43
8	REFERENCES	44
9	APPENDICES	45
9.1	Appendix 1: Pre-Specified Criteria for Adverse Events of Interest: Cholesteatoma or Neoplasm	45
9.2	Appendix 2: Pre-Specified Criteria for Adverse Events of Interest: Ototoxic symptoms (Tinnitus, Sensorineural hearing loss, Dizziness)	46
9.3	Appendix 3: Pre-Specified Criteria for Adverse Events of Interest: Otitis media or Otitis externa	47
9.4	Appendix 4: Author and Approver Signatures	48

I. LIST OF ABBREVIATIONS AND KEY TERMS

List of Abbreviations

Abbreviations	Description of abbreviations
A-B	Air bone
AE	Adverse Event
BLQ	Below the Limit of Quantification
BMI	Body Mass Index
CMQ	Custom MedDRA Query
COVID-19	Coronavirus Disease 2019
CSR	Clinical Study Report
CTMP	Chronic Tympanic Membrane Perforation
CV	Coefficient of Variation
dB	Decibels
DMC	Data Monitoring Committee
EOS	End of Study
FAS	Full Analysis Set
IAP	Interim Analysis Plan
ICE	Intercurrent Event
ICH	International Conference on Harmonization
IRT	Interactive Response Technology
LS	Least Square
MAD	Multiple Ascending Dose
MDE	Multiple Dose Expansion
MedDRA	Medical Dictionary for Regulatory Activities
MH	Mantel–Haenszel
MI	Multiple imputation
mL	Milliliter
mmHg	Millimeters of mercury
MMRM	Mixed Model Repeated Measures
MNAR	Missing Not At Random
PD1-x	Protocol Deviation 1-x
PT	Preferred Term
PTA	Pure Tone Audiometry
ROI	Region of Interest
SAD	Single Ascending Dose
SAF	Safety Analysis Set
SAP	Statistical Analysis Plan
SD	Standard Deviation

Abbreviations	Description of abbreviations
SE	Standard Error
SOC	System Organ Class
TEAE	Treatment-Emergent Adverse Event
TLF	Tables, Listings, and Figures
TMP	Tympanic Membrane Perforation
TVAS	Tinnitus Visual Analog Scale

List of Key Terms

Terms	Definition of Terms
TEAE	An adverse event (AE) observed after starting administration of the study drug through end of study visit. If an AE occurs on Day 1 and the onset check box is marked “Onset after the dose of study drug” or the onset check box is left blank, then the AE will be considered Treatment-Emergent AE.
Drug-related TEAE	Any TEAE with a causal relationship assessed as “yes” by the investigator.
Study Period	Period of time from the first study site initiation date to the last study site completing the study.

1 INTRODUCTION

This Statistical Analysis Plan (SAP) contains technical and detailed elaboration of the principal features of the analysis described in the protocol, and includes procedures for executing the statistical analysis to fulfil the objectives of the study.

The final SAP will be approved prior to database lock. Any changes to the dose escalation phase of the SAP will be approved prior to unblinding the dose escalation phase data for the prescribed interim analysis. Interim analysis plan (IAP) for the dose escalation phase will be prepared separately, and approved prior to unblinding the dose escalation phase.

Changes from the planned analyses in the final SAP that impact the statistical analyses will be documented in the Clinical Study Report (CSR).

2 STUDY OBJECTIVE(S) AND DESIGN

2.1 Study Objective(s)

Primary objective: To evaluate the safety and tolerability of ASP0598 Otic Solution.

Secondary objective: To evaluate the efficacy of ASP0598 Otic Solution.

Exploratory objective:

To evaluate otological parameters that may correlate with efficacy outcome and pharmacokinetics of ASP0598 Otic Solution.

To evaluate the safety of ASP0598 Otic Solution.

2.2 Study Design

Details of the schedule of clinical assessments are available in the protocol.

2.3 Randomization

Dose escalation

Dose escalation will consist of up to 4 cohorts for single ascending dose (SAD) and up to 2 cohorts for multiple ascending dose (MAD). In each cohort of the SAD, a total of 5 subjects will be randomized in a 4:1 ratio of ASP0598 Otic Solution and placebo. In each cohort of the MAD, a total of 8 subjects will be randomized in a 3:1 ratio of ASP0598 Otic Solution and placebo.

For each cohort in SAD and MAD, a simple block randomization schedule will be generated.

Dose expansion

The decision to open the single and multiple dose expansion phases will be based on the safety and efficacy results of the interim analyses after completion of SAD and after completion of MAD, respectively.

Up to 39 subjects will be randomized to each of the single dose and/or multiple dose expansion phases of the study. Based on the interim analysis results,

- If 3 treatment groups are selected, approximately 39 subjects will be randomized in a 1:1:1 ratio of high dose ASP0598 otic solution, low dose ASP0598 otic solution and placebo (13 subjects in each treatment group).
- If 2 treatment groups are selected, approximately 26 subjects will be randomized in a 1:1 ratio of high dose ASP0598 otic solution (13 subjects) or placebo (13 subjects).

Stratification at the time of randomization will be based on the % size of the TMP ($\leq 15\%$, $> 15\%$) and subjects will be balanced equally between the treatment groups.

For all phases subjects may be replaced at the discretion of the sponsor. If replaced, the replacement subject will be given the same treatment group as the original subject's randomized treatment group. Randomization will be performed via interactive response technology (IRT) using central allocation. If a subject is assigned a randomization number, but does not receive study drug, the randomization number will not be used again. Specific procedures for randomization through the IRT are contained in the study-specific IRT manual.

3 SAMPLE SIZE

SAD and MAD

Formal sample size calculations were not performed. The dose escalation phase is not intended to show statistical difference between ASP0598 Otic Solution and placebo subjects.

A sample size of 5 per cohort ($n = 4$ ASP0598 Otic Solution, $n = 1$ placebo) for SAD and 8 per cohort ($n = 6$ ASP0598 Otic Solution, $n = 2$ placebo) for MAD is based on precedent set by other clinical studies of similar nature. The number of subjects and study procedures planned for this clinical study are considered reasonable to achieve the clinical study objectives.

Dose expansion

Assuming the complete closure rate in placebo and ASP0598 higher concentration group are 10% and 80% respectively, eleven (11) subjects per treatment group will provide more than 90% power to detect a statistically significant difference at a 2-sided significance level of 0.05. Considering the drop-out rate of 10%, 13 subjects per treatment group will be enrolled (nQuery Advisor 7.0).

4 ANALYSIS SETS

In accordance with International Conference on Harmonization (ICH) recommendations in guidelines E3 and E9, the following analysis sets will be used for the analyses.

The determination of whether subjects are included or excluded from the safety and efficacy analysis sets will be made prior to database lock. For the dose escalation phase, the determination will be made prior to finalization of relevant programming activities for the prescribed interim analysis.

4.1 Full Analysis Set

The full analysis set (FAS) will consist of all randomized subjects who receive a dose of

study drug and have baseline value and at least 1 post baseline complete closure assessment during study period. This will be the primary analysis set for efficacy analyses.

In the analyses of FAS, subjects will be presented by randomized (planned) treatment group even if the treatment they received was different.

For study period, post baseline values will not contribute to the FAS as shown below:

- SAD: if the study day of the value is > minimum(study day of end of study visit, 57) + 7 days.
- Single dose expansion and MAD: if the study day of the value is > minimum(study day of end of study visit, 85) + 7 days.
- Multiple dose expansion: if the study day of the value is > minimum(study day of end of study visit, 113) + 7 days.

4.2 Safety Analysis Set

The safety analysis set (SAF) consists of all randomized subjects who receive a dose of study drug. The SAF will be the primary analysis set for the safety data and pharmacokinetic data.

In the analyses of SAF, subjects will be presented by actual treatment received.

For MAD and multiple dose expansion, actual treatment will be the same as planned treatment if the subject receives randomized treatment for the entire treatment duration. Otherwise, actual treatment will be the treatment corresponding to the first treatment actually received.

5 EFFICACY AND SAFETY ENDPOINTS

5.1 Primary Safety Endpoint(s)

- Treatment-emergent adverse events (TEAEs)
 - **TEAE:** an AE observed after starting administration of the study drug through end of study visit. If an AE occurs on Day 1 and the onset check box is marked “Onset after the dose of study drug” or the onset check box is left blank, then the AE will be considered TEAE. Refer to Section [6.9.1](#) for end day of end of study visit definition.
 - **Drug-related TEAE:** any TEAE with a causal relationship assessed as “yes” by the investigator. If the relationship is missing then it is considered as drug-related.

Imputed date for AE onset date may be used to determine TEAE (Section [6.9.3.1](#)).

The investigator will use the following definitions to rate the severity of each AE:

- Mild
- Moderate
- Severe

- Incidence of AEs of special interest will be defined as shown below.
 1. Cholesteatoma or neoplasm
 2. Ototoxic symptoms (tinnitus, sensorineural hearing loss, dizziness)
 3. Otitis media or otitis externa

AEs of special interest will be identified using custom MedDRA queries (CMQs). Detailed information about AEs of special interest is provided in Appendices 1, 2 and 3.

- Change from baseline in bone conduction hearing at 1, 2, 4 kHz by Pure Tone Audiometry (PTA)

A lower value indicates better level of hearing.

For the change from baseline, a negative value (decrease from baseline) indicates improvement (i.e., better level of hearing).

Mean bone conduction hearing (dB):

Arithmetic mean of the values at 1, 2 and 4 kHz. If the value is missing for any of the 3 frequencies, then the mean value will be set to missing.

- Change from baseline in Tinnitus Visual Analog Scale (TVAS)

The TVAS is a numeric scale and ranges from 0 (not at all strong or loud) to 10 (extremely strong or loud). A lower value indicates less level of discomfort.

For the change from baseline, a negative value (decrease from baseline) indicates improvement (i.e., less level of discomfort).

TVAS may be reported for one of the following areas: ear (left, right or bilateral) or other.

At a time point, if a subject did not experience tinnitus, TVAS will be reported as 0. In this case, the TVAS will be considered as 0 for all two areas.

At a time point, if a subject experiences tinnitus, the result will be reported with a value ranging from 1 to 10 for one of the areas. In this situation, the TVAS result will be imputed as 0 for the other areas [e.g., if TVAS = 3 for the ear (left) then TVAS will be imputed as 0 for ear (right) and other. if TVAS = 3 for the ear (bilateral) then TVAS will be imputed as 3 for ear (left) and ear (right) and 0 for other].

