9.5 Analysis of Safety

Safety analysis will be conducted using the SAF, unless otherwise specified.

The primary endpoints to evaluate the safety and tolerability of ASP0598 Otic Solution are shown below:

- TEAEs
- Incidence of AEs of special interest:
 1. Cholesteatoma or ear neoplasm
 2. Ototoxic symptoms (tinnitus, sensorineural hearing loss, dizziness)
 3. Otitis media or otitis externa
- Change from baseline in bone conduction hearing at 1, 2, 4 kHz by PTA
- Change from baseline in TVAS

No statistical hypothesis testing will be performed.

Continuous data will be summarized using descriptive statistics and categorical data will be summarized using number and percentage of subjects.

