6.5.3 Tinnitus Visual Analog Scale (TVAS)

Descriptive statistics will be used to summarize the treated ear TVAS baseline value, post baseline value and change from baseline at each specified post baseline analysis visit by treatment group. Refer to Section 6.5.2 for the list of analysis visits. Number and percentage of subjects will be used to summarize an increase from baseline for the TVAS at each specified post baseline analysis visit by treatment group.

- An increase in tinnitus in any ear.
- An increase in tinnitus in treated ear.

Analysis visits:

SAD	Day 2 to Week 2, Day 2, Day 3 ^a , Week 1, Week 2, Week 4, Week 8 and Maximum*
Single dose expansion	Day 2 to Week 2, Week 2, Week 4, Week 8, Week 12 and Maximum ^b
MAD	Day 2 to Week 2, Week 1, Week 2, Week 3, Week 4, Week 5, Week 8, Week 12, EOS and Maximum ^b
Multiple dose expansion	Day 2 to Week 2, Week 2, Week 4, Week 6, Week 8, Week 12, Week 16, EOS and Maximum ^b

For Day 2 to Week 2, maximum post baseline value during the analysis window will be used.

^a Day 3 evaluations will only be performed for cohorts 1, 2 and 3.

^b Maximum post baseline value during study period.

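### Tinnitus scored under 'other' enters no TVAS summary in SAP 6.5.3, so new or louder tinnitus reported there shows as no change or as a decrease

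*SAP*

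**What the plan says.** Protocol 3.1 and 9.5 list "Change from baseline in TVAS" (given in full as the Tinnitus Visual Analog Scale in 3.1) among the primary safety endpoints. Neither section specifies an ear or area. SAP 5.1 supplies that detail: "TVAS may be reported for one of the following areas: ear (left, right or bilateral) or other". The scale "ranges from 0 (not at all strong or loud) to 10 (extremely strong or loud"), and for the change from baseline "a negative value (decrease from baseline) indicates improvement (i.e., less level of discomfort").

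A subject without tinnitus scores 0 everywhere. A subject with tinnitus gives a score of 1 to 10 for one area, and "the TVAS result will be imputed as 0 for the other areas". Two examples follow. In the first, "if TVAS = 3 for the ear (left) then TVAS will be imputed as 0 for ear (right) and other". In the second, 3 is reported for bilateral, "then TVAS will be imputed as 3 for ear (left) and ear (right) and 0 for other". There is no example for a report under 'other', and no exception for it.

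SAP 6.5.3 gives descriptive statistics for the treated ear only (baseline, post-baseline and change). It then counts subjects in two rows: "An increase in tinnitus in any ear", and an increase in the treated ear. The 'other' score appears in none of these.

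**The concern.** The imputation rule and the choice of summaries are each defensible alone. Together they remove a collected score from a primary safety endpoint. A report under 'other' sets both ears to 0, and only ears are tabulated.

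Three things can follow. New tinnitus, or louder tinnitus already located under 'other', shows as no change. If the treated ear had a non-zero baseline, the same report shows as a decrease, which SAP 5.1 labels improvement. A move from 'other' to the treated ear shows as a worsening even when the reported score has fallen. With 4 to 13 subjects per active group, one such subject can change the sign of a group mean.

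**Working it through.** **Inputs.** The rule, its two examples, the 0 to 10 range and the direction of change come from SAP 5.1. The tabulated quantities come from SAP 6.5.3. Active group sizes are 4 (SAD), 6 (MAD) and 13 (expansion), from SAP 2.3 and 3. The individual scores below are assumed for illustration; the documents give none.

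**Rule.** A score v reported for left, right or other is assigned to that area, with 0 elsewhere. A bilateral score v gives left = right = v and other = 0. Treated-ear change = post-baseline minus baseline for that ear. The any-ear count is taken as true if either the left or the right ear exceeds its own baseline.

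**Reproducing the SAP's examples.** Left 3 gives left 3, right 0, other 0. Bilateral 3 gives left 3, right 3, other 0. Both match.

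**Applying the rule to 'other'** (treated ear = left):

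| Baseline | Post-baseline | Treated-ear change | Increase, any ear | Increase, treated ear | Change in reported score |
|---|---|---|---|---|---|
| left 3 | other 8 | 0 - 3 = -3 | No | No | 8 - 3 = +5 |
| bilateral 3 | other 8 | 0 - 3 = -3 | No | No | +5 |
| none (0) | other 8 | 0 - 0 = 0 | No | No | +8 |
| other 3 | other 8 | 0 - 0 = 0 | No | No | +5 |
| other 8 | left 3 | 3 - 0 = +3 | Yes | Yes | -5 |
| left 3 | right 8 | 0 - 3 = -3 | Yes | No | +5 |

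The last row shows that the any-ear count does catch a shift to the opposite ear. It cannot catch a shift to 'other', because both ears are then 0.

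**Generality.** For a treated-ear baseline b from 1 to 9 and any higher integer score under 'other', there are 9 + 8 + ... + 1 = 45 pairs. All 45 give a treated-ear change of -b and trigger neither count.

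**Effect on a group mean.** Take one subject as in the first row and no change in the others:

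- n = 4: -3/4 = -0.75 as tabulated; +5/4 = +1.25 as reported.
- n = 6: -3/6 = -0.50; +5/6 = +0.83.
- n = 13: -3/13 = -0.23; +5/13 = +0.38.

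These show what one subject can do. They do not estimate how often it happens.

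**The case against.** The strongest reply is that the 0 may be correct. Left, right and both ears each have their own option, so a subject who picks 'other' has arguably said that the tinnitus is not in the treated ear. A reader might infer that the rule puts an error of up to 10 points into the treated-ear score. That holds only if 'other' can include treated-ear tinnitus, and the documents do not say so.

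A reader might also infer that the SAP departs from an area-free endpoint defined in the protocol. It does not: the protocol is silent on area, and SAP 1 describes the SAP as the detailed elaboration of the protocol. A treated-ear focus also fits a product applied to one ear, with post-baseline audiometry, microscopy and imaging confined to that ear.

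A third tempting reading is that an ototoxic signal would be hidden. The documents do not support that. Tinnitus recorded as an adverse event is counted as an event of special interest whatever its location (SAP 5.1, 6.5.1 and Appendix 2). Bone conduction is summarised separately (SAP 6.5.2). The blinded escalation review includes TVAS, and the stopping rules include clinically significant reports of tinnitus (Protocol 4.1.1.2 and 4.1.1.3). No hypothesis test depends on TVAS (Protocol 9.5).

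All of this limits the weight of the point. It does not answer the point itself. Even if 0 is right for the treated ear, a louder score given by the subject still reaches no TVAS summary. The adverse-event route depends on an event being recorded, whereas TVAS is collected at every visit as an endpoint in its own right. SAP 6.5.3 already looks beyond the treated ear with its any-ear row, but stops short of 'other'.

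**Conclusion.** The point holds as a gap confined to the TVAS summaries. As written, SAP 5.1 and 6.5.3 leave every score reported under 'other' out of the summaries of a primary safety endpoint. New or worsening tinnitus there is tabulated as no change, or as a decrease when the treated ear had a non-zero baseline (alone or through a bilateral score). A move from 'other' to the treated ear can appear as a worsening.

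For one subject with the assumed scores, the tabulated change is -3 against a reported +5, enough to reverse the sign of the mean in active groups of 4, 6 or 13 when no one else changes. The overall effect cannot be computed, because the frequency of 'other' is not given. The conclusion rests on applying the general imputation sentence to 'other', which the text does not exempt. It does not require the treated-ear 0 to be wrong. This is a low-cost improvement to descriptive safety reporting and changes no formal conclusion of the trial.

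**What to change.** In SAP 6.5.3:

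- Add a by-visit summary of the reported TVAS score and its change from baseline, regardless of area.
- Add a count of subjects with an increase in tinnitus in any area (left, right, bilateral or other).
- Keep the treated-ear rows, with a footnote giving the number of subjects at each visit whose treated-ear 0 comes from a report under 'other'. The added rows alone would leave the -3 in the example unexplained; the footnote shows where such values come from.

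In SAP 5.1, state what 'other' means, and reconcile the reference to 'all two areas' with the next paragraph, which treats left, right and other as three.

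The cost is a few extra descriptive rows per visit in each of the four study parts, from data already collected. The drawback is that the area-free rows include tinnitus in the untreated ear, so they should be read beside the treated-ear rows and not in place of them.
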